### 6.1.5 Secondary Efficacy Analyses

#### 1) WOMAC Score

- ① Change of WOMAC score from baseline at Month 6 (JointStem group vs. positive control group)  
; This secondary efficacy endpoint will be analyzed with an ANCOVA with factors of treatment and the baseline of WOMAC score as a covariate. Model-based LS Means of the differences between study and control groups, along with 95% CI and p-value will be provided.
- ② Change of WOMAC score from baseline at Months 9 and 12 (JointStem group)  
; Change of WOMAC score from baseline at Months 9 and 12 will be analyzed using paired t-test. If change of WOMAC score from baseline at Months 9 and 12 doesn't satisfy normal distribution, Wilcoxon signed rank test will be performed.

#### 2) VAS Score

- ① Change of VAS score from baseline at Month 6 (JointStem group vs. positive control group)  
; This secondary efficacy endpoint will be analyzed with an ANCOVA with factors of treatment and the baseline of VAS score as a covariate. Model-based LS Means of the differences between study and control groups, along with 95% CI and p-value will be provided.

② Change of VAS score from baseline at Months 9 and 12 (JointStem group)  
; Change of VAS score from baseline at Months 9 and 12 will be analyzed using paired t-test. If change of VAS score from baseline at Months 9 and 12 doesn't satisfy normal distribution, Wilcoxon signed rank test will be performed.

### 3) MRI

① Comparison of MRI improvement evaluations between at Month 6 and at Month 12 (JointStem group)  
; MRI improvement evaluation at Month 12 compared to Month 6 will be analyzed using McNemar test or Bowker's test.

### 4) Lysholm Knee Scoring Scale

① Change of Lysholm Knee Scoring Scale from baseline at Month 6 (JointStem group vs. positive control group)  
; This secondary efficacy endpoint will be analyzed with an ANCOVA with factors of treatment and the baseline of Lysholm Knee Scoring Scale as a covariate. Model-based LS Means of the differences between study and control groups, along with 95% CI and p-value will be provided.

② Change of Lysholm Knee Scoring Scale from baseline at Months 6, 9 and 12 (JointStem group)  
; Change of Lysholm Knee Scoring Scale from baseline at Months 6, 9 and 12 will be analyzed using paired t-test. If change of Lysholm Knee Scoring Scale from baseline at Months 6, 9 and 12 doesn't satisfy normal distribution, Wilcoxon signed rank test will be performed.

### 5) KOOS

① Change of KOOS from baseline at Month 6 (JointStem group vs. positive control group)  
; This secondary efficacy endpoint will be analyzed with an ANCOVA with factors of treatment and the baseline of KOOS as a covariate. Model-based LS Means of the differences between study and control groups, along with 95% CI and p-value will be provided.

② Change of KOOS from baseline at Months 6, 9 and 12 (JointStem group)

; Change of KOOS from baseline at Months 6, 9 and 12 will be analyzed using paired t-test. If change of KOOS from baseline at Months 6, 9 and 12 doesn't satisfy normal distribution, Wilcoxon signed rank test will be performed.

6) IKDC

- ① Change of IKDC from baseline at Month 6 (JointStem group vs. positive control group)  
; This secondary efficacy endpoint will be analyzed with an ANCOVA with factors of treatment and the baseline of IKDC as a covariate. Model-based LS Means of the differences between study and control groups, along with 95% CI and p-value will be provided.
- ② Change of IKDC from baseline at Months 6, 9 and 12 (JointStem group)  
; Change of IKDC from baseline at Months 6, 9 and 12 will be analyzed using paired t-test. If change of IKDC from baseline at Months 6, 9 and 12 doesn't satisfy normal distribution, Wilcoxon signed rank test will be performed.

7) RAND-36 Score

- ① Change of RAND-36 Score from baseline at Month 6 (JointStem group vs. positive control group)  
; This secondary efficacy endpoint will be analyzed with an ANCOVA with factors of treatment and the baseline of RAND-36 Score as a covariate. Model-based LS Means of the differences between study and control groups, along with 95% CI and p-value will be provided.
- ② Change of RAND-36 Score from baseline at Months 6, 9 and 12 (JointStem group)  
; Change of RAND-36 Score from baseline at Months 6, 9 and 12 will be analyzed using paired t-test. If change of RAND-36 Score from baseline at Months 6, 9 and 12 doesn't satisfy normal distribution, Wilcoxon signed rank test will be performed.

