#### 6.1.3 Significance Level

The primary efficacy hypothesis tests will be performed using a 5% significance level (but, for the MRI improvement evaluation, it shall meet the validity criteria). For the secondary efficacy endpoints, hypothesis tests will be performed individually at the 5% significance level. All hypothesis tests except for the primary efficacy hypothesis tests will be performed with two-sided alternative hypotheses.

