## **6.2 Determination of Sample Size**

There was no formal sample size calculation since this is a proof-of-concept study and is not a hypothesis-driven study. The number of enrolled subjects is predefined at n=30, for 20 subjects per study group and 10 subjects per control group.

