## Appendix 8. RAND 36 Questionnaires

Site No: \_\_

Subject No: \_\_ \_\_

Subject Initials: \_\_ \_\_ \_\_

Visit (circle one): Baseline M3 M6 M9 M12 ET ( / / ) Final FU ( / / )

1. In general, would you say your health is: (circle one)  
Excellent (1) Very good (2) Good (3) Fair (4) Poor (5)
2. **Compared to one year ago**, how would you rate your health in general now? (circle one)  
Much better now than one year ago (1) Somewhat better now than one year ago (2)  
About the same as one year ago (3) Somewhat worse than one year ago (4)  
Much worse than one year ago (5)

The following items are about activities you might do during a typical day. Does **your health now limit you** in these activities? If so, how much? (circle one number on each line)

ACTIVITIES	Yes, Limited A Lot	Yes, Limited A Little	No, Not Limited At All
3. Vigorous activities , such as running, lifting heavy objects, participating in strenuous sports	1	2	3
4. Moderate activities , such as moving a table, pushing a vacuum cleaner, bowling, or playing golf	1	2	3
5. Lifting or carrying groceries	1	2	3
6. Climbing several flights of stairs	1	2	3
7. Climbing one flight of stairs	1	2	3
8. Bending, kneeling or stooping	1	2	3
9. Walking more than a mile	1	2	3
10. Walking several blocks	1	2	3
11. Walking one block	1	2	3
12. Bathing or dressing yourself	1	2	3

During the **past 4 weeks**, have you had any of the following problems with your work or other regular daily activities **as a result of your physical health**? (circle one number on each line)

	Yes	No
13. Cut down on the amount of time you spent on work or other activities	1	2
14. Accomplished less than you would like	1	2
15. Were limited in the kind of work or other activities	1	2
16. Had difficulty performing the work or other activities (for example, it took extra effort)	1	2

During the **past 4 weeks**, have you had any of the following problems with your work or other regular daily activities **as a result of any emotional problems** (such as feeling depressed or anxious)? (circle one number on each line)

	Yes	No
17. Cut down the amount of time you spent on work or other activities	1	2

18. Accomplished less than you would like	1	2
19. Didn't do work or other activities as carefully as usual	1	2

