6.2.7 RAND-36 Score

RAND-36 Score (Physical Functioning, Role Limitation (Physical), Role Limitation (Emotional), energy/Fatigue, Emotional well-being, Social Functioning, Pain, General Health) at Visits 3, 5, 6, 7 and 8 (Baseline, M3, M6, M9 and M12) or Early Termination (only if the subject is early terminated after Visit 3) or Final Follow-up Visit. Summary statistics of RAND-36 Score will be presented by visit and treatment group. The change from baseline will also be calculated and represented in summary table.

- ① Change of RAND-36 Score from baseline at Month 6 (JointStem group vs. positive control group)

This secondary efficacy endpoint will be analyzed with an ANCOVA with factors of treatment and the baseline of RAND-36 Score as a covariate. Model-based LS Means of the differences between study and control groups, along with 95% CI and p-value will be provided.

- ② Change of RAND-36 Score from baseline at Months 6, 9 and 12 (JointStem group)

Change of RAND-36 Score from baseline at Months 6, 9 and 12 will be analyzed using paired t-test (two-sided test, $\alpha=0.05$) with the null hypothesis equal to zero. The number of patients, mean, standard deviation, minimum (min) and maximum (max) values for the baseline, months 6, months 9, months 12 and change from baseline will be calculated and reported in summary table. The 95% CI and p-value will also be provided. Shapiro-Wilks test will be used to test the normality of change of RAND-36 Score from baseline at Months 6, 9 and 12. If change of RAND-36 Score from baseline at Months 6, 9 and 12 doesn't satisfy normal distribution, Wilcoxon signed rank test will be performed.

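### RAND-36 General Health includes a one-year transition item, so its change from baseline at Month 12 can differ from zero in subjects whose health is stable

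*Protocol*

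**What the plan says.** Protocol 6.1.5, item 7, plans a within-group analysis of the JointStem arm: "Change of RAND-36 Score from baseline at Months 6, 9 and 12 will be analyzed using paired t-test". SAP 6.2.7 makes the test two-sided at 5%, "with the null hypothesis equal to zero", with a Wilcoxon signed rank test as fallback: "Shapiro-Wilks test will be used to test the normality of change of RAND-36 Score from baseline at Months 6, 9 and 12". Under Protocol 6.1.3, secondary "hypothesis tests will be performed individually at the 5% significance level".

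The protocol text refers only to a RAND-36 score. The SAP names the scales, and its list ends "Emotional well-being, Social Functioning, Pain, General Health) at Visits 3, 5, 6, 7 and 8".

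Appendix 8 gives the scoring. Item 2 asks the subject, relative to one year before, "how would you rate your health in general now". Its five answers, from much better to much worse, score 100, 75, 50, 25 and 0, so an answer of no difference scores 50. General Health is the total of items 1, 2, 33, 34, 35 and 36 divided by 6. Neither document removes item 2 or treats it separately.

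Control subjects return only up to Visit 6 (Protocol 3.5.8), so at Months 9 and 12 the paired test is the only RAND-36 analysis. Protocol 6.2 sets the numbers "for 20 subjects per study group and 10 subjects per control group".

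**The concern.** Five of the six General Health items describe the subject's present health or outlook. Item 2 describes a trend over the past year. At baseline it covers the year before injection; at Month 6, about six months either side of injection; at Month 12, the year since injection. The difference between a follow-up answer and the baseline answer therefore compares trends over two different periods.

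A paired test against zero is meant to reject at its nominal rate when health has not changed. Here a subject who got worse before enrolment and has been level since can score higher at Month 12 than at baseline without any gain. A subject who was improving before enrolment and then levelled off can score lower without any loss. At Months 9 and 12 no concurrent control is available to reveal the drift. At stake is whether a significant General Health change in the JointStem arm, in either direction, can be read as a change in health.

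**Working it through.** The documents give no power figure, SD or expected value for this scale, so there is no plan figure to reproduce.

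**Scoring check.** The Appendix 8 scales use 10 + 4 + 3 + 4 + 5 + 2 + 2 + 6 = 36 items. All 36 are used, item 2 enters General Health only, and the divisor 6 counts it.

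**Shift in one stable subject at Month 12.** Baseline is Visit 3 (Week 0), so a year before Month 12 is about the baseline visit. A subject whose health is unchanged since then should answer that it is about the same (50). With the other five items constant:

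shift in General Health = (50 − baseline item-2 score) / 6

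| Baseline item 2 | Shift |
|---|---|
| 0 | 50/6 = +8.3 |
| 25 | 25/6 = +4.2 |
| 50 | 0 |
| 75 | −25/6 = −4.2 |
| 100 | −50/6 = −8.3 |

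For example, with the other items at 50 and item 2 at 25, baseline General Health is (5 × 50 + 25)/6 = 45.8. At Month 12 it is 50.0.

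**Effect on the paired t-test at Month 12.** Inputs: n = 20 (Protocol 6.2); two-sided 5%, df = 19, critical t = 2.093; no true change. Assumed, because the documents give neither: an SD of General Health change of 10 to 15 points, and the mean baseline item-2 score b.

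Noncentrality = [(50 − b)/6] × √20 / SD. At b = 25 this is 4.167 × 4.472/10 = 1.863 for SD 10 and 4.167 × 4.472/15 = 1.242 for SD 15.

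| Mean baseline item 2 | Mean shift | Rejection, SD 15 | Rejection, SD 10 | Main direction |
|---|---|---|---|---|
| 25 | +4.17 | 21.9% | 42.4% | improvement |
| 35 | +2.50 | 10.9% | 18.6% | improvement |
| 40 | +1.67 | 7.6% | 10.9% | improvement |
| 45 | +0.83 | 5.6% | 6.4% | improvement |
| 50 | 0 | 5.0% | 5.0% | none |
| 60 | −1.67 | 7.6% | 10.9% | worsening |

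**Does the Wilcoxon fallback remove it?** No. Simulating the plan's rule (Shapiro-Wilk, then t or Wilcoxon) with every subject moving from 25 to 50 gave a significant improvement in 41% of trials at SD 10 and 22% at SD 15, close to the first row. With item 2 left out, the rate was 2.1–2.8% over all settings simulated (SD 6 to 15), against a nominal 2.5% in the improvement direction.

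**Other visits.** At Months 6 and 9 the look-back still includes about 6 and 3 months before injection, so the shift is only partial; no figure is put on it here. In the Month 6 ANCOVA against control, randomisation gives both arms the same expected drift.

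**The case against.** The strongest reply concerns direction and consequence. The drift has no fixed sign: it is zero at a mean baseline answer of 50 and runs against JointStem above 50. The 22–42% figure needs the average subject to say at baseline that health was somewhat worse than a year before, and nothing in the documents establishes that. Entry requires Kellgren-Lawrence grade 3–4 disease, VAS pain of at least 40 mm and a wish for injection, which makes recent decline plausible but does not show it. This stands, so a reader should not infer that the scoring favours JointStem.

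A reader might also infer that a lasting benefit would be scored as a loss at Month 24, with item 2 falling from 100 to 50. The documents do not support this. The 100 would be an answer given after injection, whereas the baseline questionnaire belongs to the injection visit itself (Protocol 4.2.3) and cannot reflect a benefit of the injection. Change from baseline does not subtract an early follow-up answer, and SAP 6.2.7 stops at Month 12.

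The reach is also narrow: one of eight scales of one secondary instrument, in a study described as proof-of-concept. An uncontrolled change at Month 12 could not be attributed to JointStem even with ideal scoring. That stands too, and it limits the severity. It does not justify the scoring: whichever way it drifts, the difference between two one-year trend ratings with different reference dates is not a change in health since baseline.

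**Conclusion.** The point holds and is minor. As scored in Appendix 8 and tested in SAP 6.2.7, General Health can move at Month 12 in subjects whose health is stable, by (50 − baseline item-2 score)/6 per subject. The scoring and the mechanism come from the documents. The rejection rates rest on assumptions: 20 analysed subjects, an SD of change of 10 to 15, a stable subject answering 50 at Month 12, and the mean baseline answer shown in each row. Over the range examined, rejection runs from the nominal 5% at a mean of 50 to 22–42% at 25, with the excess going towards worsening above 50. The documents do not say where in this range the trial lies. The effect at Months 6 and 9 is partial, the randomised Month 6 comparison is not biased on average, and no co-primary endpoint is touched.

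**What to change.** In Protocol Appendix 8 and SAP 6.2.7, score General Health as the total of items 1, 33, 34, 35 and 36 divided by 5, at every visit and in both arms. Tabulate item 2 separately by visit and arm, and do not analyse its change from baseline. A subject whose five items are unchanged then has a change of exactly zero.

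The cost is one line in each document and a scale of five items instead of six. No new assessments are needed. Totals already entered must be re-scored from the completed forms. Appendix 8 has the coordinator score on the form, and the documents do not say whether single item answers are in the eCRF, so some re-entry may be needed. Because blinding opens subject by subject after Visit 6, the change should be dated and applied uniformly.

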### 6.1.6 Safety Analyses

AE rates will be summarized by treatment group and overall, and will be broken down by severity, seriousness and relation to study drug. Statistical tests are not planned for safety variables.

### **6.1.7 Missing Data**

Last observation carried forward (LOCF) imputation method will be used for efficacy variables, but no adjustments for missing data and no imputation methods are planned for safety variables .

## **6.2 Determination of Sample Size**

There was no formal sample size calculation since this is a proof-of-concept study and is not a hypothesis-driven study. The number of enrolled subjects is predefined at n=30, for 20 subjects per study group and 10 subjects per control group.

## **6.3 Interim Analysis**

When at least 15 subjects complete 6-month visits (Visit 6, Month 6), one unblinded interim analysis can be performed to evaluate the efficacy and safety of JointStem without the suspension of subject enrollment. The details of this interim analysis will be presented in the statistical analysis plan. No adjustment on the overall alpha-level will be made, as this is not a statistically powered study.

## **6.4 Long-term Follow-up Analysis**

All efficacy variables and the history of treatments and medications, which are measured at a long-term follow-up visit (24 months after injection) will be analyzed between treatment groups to see any long-term effects of JointStem. Also, MRI results of long-term follow-up visit will be compared to previous MRI results to see any long-term effects of JointStem. The details of this long-term follow-up analysis will be presented in the statistical analysis plan.

## 7. SAFETY DATA COLLECTION, RECORDING, AND REPORTING

### 7.1 Definitions

#### 7.1.1 Adverse Events

An adverse event is defined in the 21 CFR 312.32(a) as “Adverse event means any untoward medical occurrence associated with the use of a drug in humans, whether or not considered drug related.”

An adverse event (also referred to as an adverse experience) can be any unfavorable and unintended sign (e.g., an abnormal laboratory finding), symptom, or disease temporally associated with the use of a drug, without any judgment about causality. An adverse event can arise from any use of the drug (e.g., off-label use, use in combination with another drug) and from any route of administration, formulation, or dose, including an overdose. Worsening of a pre-existing medical condition (e.g., diabetes, migraine headaches, and gout) after the drug administration should be considered an adverse event if there is either an increase in severity, frequency, or duration of the condition or an association with significantly worse outcomes.

The investigator is responsible for reviewing laboratory test results and determining whether an abnormal value in an individual study subject represents a change from baseline values. Abnormal laboratory findings without clinical significance (based on the investigator's judgment) should not be recorded as adverse events; however, laboratory value changes requiring therapy or adjustment in prior therapy are considered adverse events.

Adverse events will be reviewed continuously throughout the study.

#### 7.1.2 Serious Adverse Events

A serious adverse event (SAE) is defined as an adverse event that

- is fatal
- is life threatening (places the subject at immediate risk of death)
- requires in-patient hospitalization or prolongation of existing hospitalization
- results in persistent or significant disability/incapacity
- is a congenital anomaly/birth defect
- other significant medical hazard

**Life threatening:** The term life-threatening in the definition of ‘serious’ refers to an AE in which the subject was at risk of death at the time of the event. It does not see an AE that hypothetically might have caused death if it were more severe.

**Hospitalization:** Any adverse event leading to hospitalization or prolongation of hospitalization will be considered as ‘serious’, UNLESS at least one of the following exceptions is met:

- the admission results in a hospital stay of less than 12 hours OR
- the admission is pre-planned (i.e., elective or scheduled surgery arranged prior to the start of the study) OR
- a medical intervention that requires hospitalization (e.g., blood product transfusion or central line insertion) will be not considered a serious adverse event

However, it should be noted that invasive treatment during any hospitalization may fulfill the criteria of ‘medically important’ and as such may be reportable as a SAE dependent on clinical judgment.

**Disability** means a substantial disruption of a person’s ability to conduct normal life functions.

**Important medical event:** Any AE may be considered serious because it may jeopardize the patient and may require intervention to prevent another serious condition. As guidance for determination of important medical events see the ‘WHO Adverse Reaction Terminology – Critical Terms List’. These terms either see or might be indicative of a serious disease state.

Such reported events warrant special attention because of their possible association with a serious disease state and may lead to more decisive action than reports on other terms.

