### **3.4 Premature Termination of Study / Closure of Center**

The sponsor has the right to terminate this study, and the investigator/sponsor has the right to close a clinical site, at any time, although this should occur only after consultation between involved

parties; the IRB must be informed in any case. Should the clinical site be closed prematurely, all study materials (equipment, study medication, etc.) must be returned to the sponsor.

This study will discontinue due to medical or administrative reasons such as:

- Serious adverse events probably related to study drug administration so that the use of study drug may no longer be justifiable
- 2 or more deaths are observed during any point in the trial
- 5 or more adverse drug reactions (NCI-CTCAE  $\geq$  Grade 3) on the injected joint are observed during any point in the trial
- Significant change of benefit-risk ratio for the subjects
- Sponsor discontinues the investigation of JointStem for the treatment of osteoarthritis or determines that the doses being studied are no longer justifiable

Possible reasons for closing of a clinical site include the following:

- The investigator feels that the number or severity of adverse events is excessive
- A change of technical, administrative, or personal circumstances occurs and the conduct of the study no longer meets ICH-GCP guidelines
- In case of evident, significant non-compliance to protocol or poor data quality

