## **7.3 Serious Adverse Event Reporting Procedures**

Serious adverse events will be collected and recorded from the drug administration to 3-month follow-ups.

Serious Adverse Events, including laboratory test abnormalities fulfilling the definition of serious, after the first dose, and during follow-up period must immediately (within 24 hours of the investigator’s awareness) be reported to the person/parties as detailed in the study file. A Serious Adverse Event form must also be completed within 1 day of the investigator’s awareness and

forwarded to the designated person/parties as detailed in the study file. Each Serious Adverse Event must be followed up until resolution or stabilization by submission of updated reports to the designated person/parties.

Serious adverse events also will be collected and reported within 1 working day of discovery or notification of the event if it occurs 7 days after the last dose of study drug or after the end of the study and is thought to be possibly related to study drug.

For all deaths, available autopsy reports and relevant medical reports should be faxed to Sponsor or their designee. For this reporting process, subject assessments must be made 7 days after administration of the last dose of study drug.

If a subject is permanently withdrawn from the study because of a serious adverse event, this information must be included in the initial or follow-up Serious Adverse Event Report Form as well as the End of Study Case Report Form.

When required, and according to local law and regulations, serious adverse events must be reported to the institutional review board and Regulatory Authorities.

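### The third hospitalization exception in Protocol 7.1.2 can make an adverse event non-serious when hospitalization is its only ground for seriousness

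*Protocol*

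**What the plan says.** Protocol 7.1.2 lists the seriousness criteria. One is that the event "requires in-patient hospitalization or prolongation of existing hospitalization". The paragraph on hospitalization then says that such an event counts as serious "UNLESS at least one of the following exceptions is met". The three exceptions are a stay shorter than 12 hours, a pre-planned admission, and the following: "a medical intervention that requires hospitalization (e.g., blood product transfusion or central line insertion) will be not considered a serious adverse event".

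Two later sentences in 7.1.2 bear on this. The one directly after the exceptions says that invasive treatment in hospital may meet the medically-important criterion and "may be reportable as a SAE dependent on clinical judgment". The paragraph on important medical events says: "Any AE may be considered serious because it may jeopardize the patient and may require intervention to prevent another serious condition".

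SAE status then drives three things:
- expedited reporting under Protocol 7.3;
- the SAE overview count and the SAE table by system organ class and preferred term in SAP 7.1, with the listing in SAP 7.1.1;
- the first discontinuation reason in Protocol 3.4: "Serious adverse events probably related to study drug administration so that the use of study drug may no longer be justifiable".

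SAP 8.2 states that no DSMB is planned.

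**The concern.** The criterion and the third exception use nearly the same test. One asks whether the event required in-patient hospitalization, the other whether an intervention required hospitalization. Transfusion and central line insertion are given only as examples, so nothing in the wording sets an outer limit. Because any single exception is enough, an unplanned admission for treatment of a complication can satisfy the criterion and the exception at once, and the exception then prevails.

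Every randomized subject who reaches Visit 3 has a joint injection, so an admission for a complication of the injected knee is a relevant case. If a site applied the exception as worded, the sponsor would not receive the 24-hour report, and the SAE tables would understate hospitalized events. With about 30 subjects and no DSMB, the sponsor relies heavily on prompt SAE reports to notice a problem.

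**Working it through.** The plan gives no figure on this point, so the check sets the sections side by side.

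**Step 1. Does the exception reach an unplanned admission?** Pre-planned admission is already the second exception. The third carries no condition about timing, planning or a pre-existing condition. It therefore adds something only for admissions that were not planned beforehand.

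**Step 2. Does it reach the adverse event, or only the procedure?** Its grammatical subject is the intervention. But it sits in a list of conditions under which an adverse event leading to hospitalization stops being serious. No sentence in 7.1.2 says that the underlying event is still classed by its own seriousness. Protocol 7.2.1 asks the investigator to record a diagnosis or syndrome; that settles the name of the event and not whether it is serious.

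**Step 3. Which events are exposed?** The exceptions qualify the hospitalization criterion only.

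| Event | Status under 7.1.2 |
|---|---|
| Fatal, life-threatening, disabling, congenital anomaly, other significant hazard | SAE; exception does not apply |
| Hospitalized for an intervention, none of the above | Not an SAE through hospitalization if the exception is read literally; can be restored only by clinical judgment |
| Hospitalized, no intervention requiring it, no other exception | SAE |

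The gap is the middle row. Both restoring sentences say *may*, so a mandatory criterion becomes a site judgment.

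**Step 4. What does an exposed post-injection event lose, and what does it keep?**

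| Element | Depends on SAE status? |
|---|---|
| 24-hour report (Protocol 7.3) | Yes |
| SAE overview count and table, SAE listing (SAP 7.1, 7.1.1) | Yes |
| First discontinuation reason (Protocol 3.4) | Yes |
| Discontinuation for 2 or more deaths, for 5 or more Grade 3 or higher drug reactions on the injected joint, for benefit-risk change, or by sponsor decision (Protocol 3.4) | No |
| Treatment-emergent tables, including by severity, and listings of all AEs (SAP 7.1) | No |

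**Step 5. Scale, for illustration only.** The planned arm sizes are 20 and 10 (Protocol 6.2). The one-sided 95% exact upper limit is 1 − 0.05^(1/n) for 0 events in n, and the 95th percentile of Beta(2, n − 1) for 1 event in n.
- JointStem, 1 of 20: 5.0%, upper limit Beta(2, 19) = 21.6%. Reclassified to 0 of 20: 0%, upper limit 1 − 0.05^(1/20) = 13.9%.
- Control, 1 of 10: 10.0%, upper limit Beta(2, 9) = 39.4%. Reclassified to 0 of 10: 0%, upper limit 1 − 0.05^(1/10) = 25.9%.

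**The case against.** The strongest reply is that the exception means only that a transfusion or a line insertion is not itself an SAE, and that the bleed or infection behind it is judged in the usual way. The grammar allows this, and the request in 7.2.1 for a diagnosis fits it. The reading is plausible and may be what was intended, but the protocol does not state it. A site following the list as laid out could reach the opposite result, and the benign reading would itself need one more sentence.

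The second reply is that safeguards exist: the other seriousness criteria, the important-medical-event paragraph, continuous review of adverse events (Protocol 7.1.1) and full AE listings. This stands in part. It limits the gap to events that are serious only through hospitalization, and it means that such events lose a classification and a fast report but not their place in the data. It does not close the gap, because the routes back to SAE status are optional.

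The third reply is that the numbers in the illustration would follow from any misclassified event. That is correct. They show how little it takes to change the safety statement in a trial of this size, and say nothing about how likely this exception is to cause it. The SAP plans no such bound and no safety tests.

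**Conclusion.** The concern holds in a limited form. As written, 7.1.2 contains a rule which, followed literally, removes SAE status from a hospitalized event whose only ground for seriousness is the hospitalization. This is wrong as written and not just a missing detail. The conclusion assumes a post-injection event within the SAE collection period of Protocol 7.3, an admission for an intervention that required it, and a site that applies the list literally and does not use its discretion. The frequency is unknown; the consequence per event is the loss set out in the comparison above.

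A reader might infer more than the documents support:
- *That the most severe complications drop out.* They do not. Fatal, life-threatening and disabling events stay serious under criteria that the exception does not touch.
- *That the stopping rules are disabled.* Only one of the five reasons in Protocol 3.4 uses SAE status, and it has no numeric threshold. A Grade 3 or higher drug reaction in the injected knee still counts towards the joint-reaction reason.
- *That a bleed after liposuction shows the defect.* It does not isolate it. Liposuction is at Week -5. Protocol 7.2 starts AE reporting after the first dose and 7.3 starts SAE collection at drug administration, while 3.6.3 collects AEs at all visits after randomization. That is a separate inconsistency, and a pre-injection event could be missed with or without this exception.
- *That the exclusion criteria on bleeding and infection state these as treatment risks.* They are eligibility screens, and calling them risks of the study procedures is an inference.

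**What to change.** In Protocol 7.1.2, either delete the third exception, or reword it so that only the procedure itself is not recorded as an SAE, while the adverse event that led to hospitalization is classed by its own seriousness and recorded under its diagnosis (the bleed, for example, and not the transfusion). Bring the SAE form instructions into line. The SAP needs no change, because its tables follow the SAE classification.

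The cost is a short protocol amendment and a note to sites. The SAE count may be slightly higher. The change concerns classification and reporting only and leaves the treatment of subjects as it is. The differing start dates for AE and SAE collection in 3.6.3, 7.2 and 7.3 should be reconciled separately.
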